## Design & Procedures

- Describe the study, providing detail regarding the study intervention (drug, device, physical procedures, manipulation of the subject or the subject's environment, etc.). Discuss justifications for placebo control, discontinuation or delay of standard therapies, and washout periods if applicable. Identify procedures, tests and interventions performed exclusively for research purposes or more frequently than standard of care. Include alternative therapies, concurrent therapies discontinued per protocol, risk benefit ratio, and use of tissue/specimens. Discuss monitoring during washout periods if applicable. Include brief description of follow-up, if any.

**Study design.** The present study will be a prospective open-label pilot study to help establish feasibility, safety and enable dose finding for BTX. The schedule of events is presented in **Figure 3**. Following a baseline invasive (right heart catheterization) cardiopulmonary exercise testing (CPX) patients will undergo unilateral celiac plexus block (**Figures 2 and 4**), followed by repeat hemodynamic testing in the following 90 minutes. Repeat CPX (with and without hemodynamic testing) will occur at 2, 4, 8 weeks. A 12 month phone call to investigate vital status, HF hospitalizations will conclude the study. Functional testing at baseline and follow up will be supplemented by a series of minimally invasive and non-invasive measures of static and dynamic blood volume distribution (radionuclear plethysmography, bioelectrance, hepatic vein ultrasound), congestion parameters (biomarkers, BVA), autonomic nervous tone (catecholamines,

baroreflex, and heart rate variability) and symptom questionnaires (Likert and Visual Analog scale). Given high volume of patients and right heart catheterizations (>1,000 per year) and our experience with enrolling patients in the preliminary studies, we anticipate to complete recruitment within 2 years.

Figure 2. Splanchnic Nerve Block Procedure (A) and Prior Data of Nerve Blockade in Acute (B) and Chronic Heart Failure (C). \* indicates p<0.05

[figure not shown]

Figure 3. Study Flow

[figure not shown]

Figure 4. Study set-up: Invasive hemodynamic testing

[figure not shown]

Table 1: Schedule of events (CS, clinical study; SOC, standard of care/clinical)

Required Assessment	Pre-Procedure (Day 1)	Baseline (Intra-Procedure)	Block	Post-Block Procedure	48 Hour	Week 1	Week 2	Week 4	Week 8	Month 6	Month 12

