Vitals (BP, HR, RR, SpO 2 , weight)	X (CS)			X(CS)		X(CS)	X(CS)	X(CS)			
Orthostatic vitals	X(CS)			X(CS)		X(CS)	X (CS)	X (CS)			
Non-Invasive Testing*	X(CS)			X(CS)		X(CS)	X (CS)	X (CS)			
Pregnancy test	X (SOC)										
Labs: BMP (SOC), pro-BNP (CS), CA-125 (CS), urine sodium (CS),	X (CS /SOC)			X (CS /SOC)		X (CS /SOC)	X (CS /SOC)	X (CS /SOC)			
Labs Renin, Angiotensin II, Vasopressin, Plasma Catecholamines	X (CS)			X (CS)		X (CS)	X (CS)	X (CS)			
				X(CS)	X(CS)				X(CS)	X(CS)	

Dyspnea and EQ-5D-3L Questionnaires	X (CS)		X(CS)		X(CS)	X (CS)	X(CS)		
Six minute walk test	X (CS)		X(CS)		X(CS)	X (CS)	X(CS)		
Blood volume - Daxor	X (CS)					X (CS)			
Heart rate variability	X (CS)	X (CS)	X (CS)		X (CS)	X (CS)	X (CS)		
Right Heart Cath (RHC)		X (CS, SOC)				X (CS)			
Scintigraphy	X (CS)					X (CS)			
Invasive CPX (peak VO2)		X (CS)				X (CS)			
CPX (peak VO2)					X (CS)		X (CS)		
Echocardiogram		X (CS)	X (CS)		X (CS)	X (CS)	X (CS)		
Renal ultrasound (to be done by [name])	X (CS)		X (CS)		X (CS)	X(CS)	X (CS)		
Splanchnic nerve block			X (CS)						
Phone Call				X (CS)	X (CS)			X (CS)	X (CS)

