### Testing procedures

**Blood volume analysis and scintigraphy:** Blood volume analysis will be performed using I131-radiolabelled albumin. The injection of the drug and associated blood draws will be completed in the nuclear lab. Patients will have a baseline blood sample drawn (4ml). Then, patients will be injected the radiolabeled albumin. After 12, 16 and 20 minutes we draw additional blood samples. The blood samples will be processed at the Duke nuclear laboratory using the Daxor analyzer or sent to Daxor Inc. for processing. If sent to Daxor for processing we will only share deidentified blood samples. Samples will be labelled with case number. We will provide patients age, gender and weight, which are needed for data calculation.

Following injection of the agent, the patient will also receive a **MUGA Scan** (Multiple Gated Acquisition scan) is a noninvasive tool for assessing the function of the heart. The **MUGA scan** produces a moving image of the beating heart but also allows to image the abdomen, and from this image several important features can be determined about the health of the cardiac ventricles and blood distribution.

Following injection of the technetium99, patients will be placed under a scintigraphy camera which will pick up the counts of radiation over the chest and abdomen. We will record resting counts over both compartments (chest /abdomen). Then patient will perform up to 5 min low resistance leg exercise while supine on a stepper placed at bed end. Counts will be recorded over both compartments during exercise.

Blood draws reported above will occur during resting recording. The exercise will occur after the 20 min blood draw is complete. Total duration of the study is anticipated to be 30 min.

The I-131 (Volumex) will either be administered by the nuclear medicine technician or [name]. Both have received training from the manufacturer.

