**Nerve Block Procedure.** The unilateral, left-sided, temporal bilateral celiac plexus block will be performed by the interventional pain specialty team in the catheterization laboratory, with continuous hemodynamic monitoring similarly to our previously published experience. The celiac plexus block will be performed under fluoroscopic guidance in the posterior chest wall (vertebral space L1) to guarantee maximal safety (**Figure 2**). We will use a mix of 3 ml of lidocaine 1.55 with 1:10000 epinephrine, 10 ml of 0.5% ropivacaine and up to 1.5 U/kg of BTX Type A. Lidocaine with epinephrine is used for procedural

safety to exclude intravascular injection. In the present study we will start at a lower dose of the BTX (dose finding). We will plan to increase dose or decrease per Kg unit doses for Botox based on 4 week assessment.

The dosing up titration scheme (Scenario 1) is as following:

1. The 1st and 2nd subject receiving the block splanchnic procedure - 75Units of Botox, (not more than 1.5 Units/kg) follow up at 2 weeks with CPX and 4 weeks with invasive CPX and 8 weeks with CPX
2. The 3rd and 4th subject receiving the block splanchnic procedure - if prior dose tolerated, no safety issues at 4 weeks than proceed with dose increase to: 100Units of Botox, (not more than 1.5Units/kg) follow up at 2 weeks with CPX and 4 weeks with invasive CPX and 8 weeks with CPX
3. The 5th and 6th subject receiving the block splanchnic procedure - Scenario 1: if prior dose tolerated, no safety issue and satisfactory efficacy at 4 weeks than patient 5/6 will get injection of 100Units of Botox again (not more than 1.5Units/kg) with follow up at 2 weeks with CPX and 4 weeks with invasive CPX and 8 weeks with CPX Satisfactory efficacy is defined as >25% reduction with exercise wedge pressure  
Scenario 2: if prior dose tolerated, no safety issue and efficacy not satisfactory at 4 weeks than patient 5/6 will get injection of 125Units of Botox (not more than 1.5Units/kg) with follow up at 2 weeks with CPX and 4 weeks with invasive CPX and 8 weeks with CPX.

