### Exclusion Criteria:

1. Contraindicated medications:

- Anticoagulation at the time the procedure or in case of recent warfarin use an INR >1.4. Anticoagulation includes: warfarin, or novel oral anticoagulants like dabigatran, rivaroxaban, apixaban, edoxaban or full dose intravenous heparin products or bivalirudin and fondaparinux). Antiplatelet agents besides aspirin such as ticagrelor, prasugrel, Plavix are also considered to be a contraindication if used at time point of procedure.
- Immunosuppressive medications for solid organ transplant

2. HF medication regimen: Initiation of HF medications (in the 48 hours preceding the study) such as beta blockers, ACEI, ARB, aldosterone receptor blockers, calcium channel blockers of any type, central sympatholytics like clonidine, moxonidine,

3. Recent acute MI or hemodynamic instability:

- Acute MI (STEMI or Type I NSTEMI) within 7 days.
- Evidence of progressive cardiogenic shock within 48 hours

4. Certain forms of HF:

- Restrictive cardiomyopathy
- Constrictive pericarditis
- Pericardial effusion with evidence of tamponade
- Severe valvular stenosis requiring intervention

5. Severe bleeding risk:

- Known history of an increased bleeding risk
- Thrombocytopenia (< 50,000)

6. Significant comorbidities:

- End-stage renal disease CKD stage 5 due to primary renal pathology
- Severe scoliosis of the thoracic spine
- History of lung disease other than asthma and COPD (like interstitial fibrosis, cystic fibrosis, pneumonitis, lung cancer etc.)
- Respiratory instability (dependent on >4 L nasal cannula for a saturation >90% SpO2)

- Exclude severe fixed pulmonary hypertension
- History of organ transplant (heart , lung, liver, pancreases, small bowel).

7. Pregnancy: patients of childbearing age will be tested with pregnancy tests, unless they had a hysterectomy or removal of their ovaries.

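### Table 1 schedules one pregnancy test but two research radionuclide sessions, so in the supplied text the second session has no pregnancy check

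*Combined protocol and SAP*

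**What the plan says.** Pregnancy is item 7 of the Exclusion Criteria: "Pregnancy: patients of childbearing age will be tested with pregnancy tests, unless they had a hysterectomy or removal of their ovaries". The item says who is tested, but not when or how often.

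In Table 1 (Design & Procedures), the row "Pregnancy test" carries one mark, in the Day 1 pre-procedure column, labelled standard of care. The rows "Blood volume - Daxor" and "Scintigraphy" carry two marks each: one pre-procedure and one in a later column. All four of those marks are labelled as clinical study.

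The Testing procedures section names the agents. "Blood volume analysis will be performed using I131-radiolabelled albumin", and the scintigraphy follows an injection of technetium. The dosing scheme under Nerve Block Procedure gives each pair of subjects the same visit sequence: "follow up at 2 weeks with CPX and 4 weeks with invasive CPX and 8 weeks with CPX".

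**The concern.** The protocol treats pregnancy status as relevant to entry and schedules a test at the visit with the first radionuclide session. It then plans a like session, for research purposes only, at a later visit, and the test row is empty there. A participant who conceives after Day 1, or whose pregnancy is too early to be detected on Day 1, would receive a second I-131 and technetium administration by following the schedule as written.

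What is at stake is participant and fetal safety. The point does not touch endpoints, error rates or the dose decisions.

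**Working it through.** No sample-size or power figure is involved. The check is a count of marks in Table 1, followed by dating the second session.

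**1. Count per participant of childbearing potential**

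| Item | Marks | Where | Label |
|---|---|---|---|
| Pregnancy test | 1 | Day 1 pre-procedure | standard of care |
| I-131 blood volume | 2 | Day 1 pre-procedure; one follow-up visit | clinical study, both |
| Technetium scintigraphy | 2 | Day 1 pre-procedure; same follow-up visit | clinical study, both |

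The two radionuclide rows coincide, so there are 2 sessions. One session shares a column with a test, leaving 2 − 1 = 1 session without one.

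**2. Date of the second session**

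The column positions in Table 1 were disturbed when the file was read, so the week is inferred. The second blood volume and scintigraphy marks share a position with the second right heart catheterization and the second invasive CPX, and that position lies between the two non-invasive CPX marks. The dosing scheme gives the order CPX at 2 weeks, invasive CPX at 4 weeks, CPX at 8 weeks. The shared position is therefore week 4, about 4 × 7 = 28 days after Day 1.

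Read by raw position, the mark would fall under week 1. That would also put the first non-invasive CPX before week 1, against the 2-week visit in the dosing scheme. The finding does not depend on the exact week: on either reading the mark is after the block, and the pregnancy row has nothing after Day 1.

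**3. Whether another part of the plan covers it**

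- *Standard care.* All subjects enter through an electively scheduled right heart catheterization (Selection of Subjects), and the baseline catheterization is labelled both clinical study and standard of care. That explains a standard-of-care pregnancy test on Day 1. The follow-up catheterization, blood volume and scintigraphy are labelled clinical study only, so these procedures give routine care no stated reason to test again.
- *Risk/Benefit Assessment.* It covers the nerve block. It does not discuss radionuclide exposure or a pregnancy arising during the study.
- *Data & Safety Monitoring.* The events it lists do not include pregnancy.
- *Unlabelled row in Table 1.* One row has lost its label. Its two early and two late marks resemble the telephone-call row, so there is no ground for reading it as further pregnancy testing.

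**4. Size**

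If n participants are of childbearing potential, there are 2n sessions and n tests, leaving n sessions unscreened. The supplied text gives no total sample size and no sex or age breakdown. Inclusion starts at age 18, so n can exceed zero. Over the six subjects named in the dosing scheme, n lies between 0 and 6. A value near the low end is likely in chronic heart failure, but that is an assumption.

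**The case against.** The strongest reply is that nothing here is contradictory. Exclusion 7 is an entry criterion, and Table 1 has a matching entry test. The word for tests in exclusion 7 is plural and sets no limit, the table is damaged, and the consent pages were removed from the file. A nuclear laboratory may also screen by its own routine. On this view a schedule is missing one operational line that affects few or no participants.

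Part of this stands. The single-test reading comes from Table 1, not from the wording of exclusion 7. The absence of a contraception condition can be asserted only for the supplied text. Laboratory routine cannot be checked here. None of this puts a check at the second session, and a plural noun does not schedule a repeat.

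Several stronger readings are tempting and are not supported:

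- *Half of all radionuclide sessions are unscreened.* The one-in-two ratio applies only to women of childbearing potential.
- *The second visit also brings fluoroscopy without a check.* The documents describe fluoroscopy for the nerve block and do not state it for the repeat catheterization.
- *The long botulinum toxin effect strengthens the case.* A test at week 4 cannot bear on an injection already given.
- *The first session is demonstrably protected.* Table 1 puts the test, blood volume and scintigraphy in one column without giving their order.

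**Conclusion.** The point holds in a limited form. As scheduled, the pregnancy check accompanies one of two like research exposures, and the second, inferred to be at week 4, has none in the supplied text. For each woman of childbearing potential that is one unscreened session out of two. The number of such women is not given, is probably small, and may be zero.

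The conclusion rests on two things: the marks in the pregnancy, blood volume and scintigraphy rows being complete, and no repeat check being required in pages that were removed. A reader might infer that the plan nowhere addresses contraception or pregnancy during follow-up. The documents at hand cannot show that. It is a safety correction to the schedule, worth making because it is specific and cheap, with no consequence for the statistical analysis beyond possible loss of a repeat measurement.

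**What to change.** Reconcile exclusion 7 and the pregnancy-test row of Table 1 with the second blood volume and scintigraphy session, so that the check scheduled with the first session is also scheduled for the second. Exclusion 7 should say when testing takes place. The sponsor should state what follows a positive repeat result; that rule is for the sponsor to set. If a repeat check or contraception condition already exists in the consent form or in laboratory procedure, a cross-reference in Table 1 would do.

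The cost is one table mark, a sentence in exclusion 7, and one inexpensive test per woman concerned. The visit already includes blood sampling, with a sample drawn before the I-131 injection. The downside is that a positive result may lose that participant's repeat radionuclide data, leaving one fewer before-and-after pair in a small pilot.

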#### 8. Procedure

Unable to tolerate procedure as determined by or investigator

Will be excluded if invasive hemodynamics on study date determine that the does not have elevated filling pressures at rest or stress. Following pressures/situations will exclude the : wedge pressure < 15mmHg (< 12mmHg on inotrope) at rest and < 25mmHg with peak stress (< 22 with inotropes) and greater than the central venous pressure or determined by study personnel to be at risk for nerve block related complications.

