### Inclusion Criteria:

1. Age 18-90
2. Patients with or without Cardiomems device implanted
3. Followed at DUMC for known or suspected diagnosis of HF (NYHA stage 2-3, Class C-D), including patients on inotropic medication
4. Systolic blood pressure (SBP) > 100mmHg
5. History of HF hospitalization or ER visit or IV diuretic use in the last 12 months.
6. Patients will be included regardless of left ventricular ejection fraction.

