### Data Analysis & Statistical Considerations

- Describe endpoints and power calculations. Provide a detailed description of how study data will be analyzed, including statistical methods used, and how ineligible subjects will be handled and which subjects will be included for analysis. Include planned sample size justification. Provide estimated time to target accrual and accrual rate. Describe interim analysis including plans to stop accrual during monitoring. Phase I studies, include dose escalation schema and criteria for dose escalation with definition of MTD and DLT.

[name] in the Duke Heart Center will be performing the statistics for the Splanchnic III study. We will perform descriptive statistics. Statistical comparisons will be made using t-tests for continuous outcomes and chi square or Fisher's exact test. Unless otherwise specified, a two-sided 0.05 level of significance will be used to declare change in pre-and post-procedure variables different.

There is no direct measure of technical success following attempted block of the splanchnic nerves. Procedural success to block the splanchnic nerves will be assumed in 70% of the cases based on the experience in splanchnic nerve blocks in patients with intractable cancer.

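### The wedge session that qualifies a patient is also the only scheduled pre-block baseline, so regression to the mean modestly favours the block at week 4

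*Combined protocol and SAP*

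**What the plan says.** Under Exclusion Criteria, item 8 (Procedure), a patient "Will be excluded if invasive hemodynamics on study date determine" that filling pressures are not raised. The cut-offs are "wedge pressure < 15mmHg (< 12mmHg on inotrope) at rest and < 25mmHg with peak stress (< 22 with inotropes"). The two limits are joined by a conjunction, so a patient is excluded only when both are missed. Away from inotropes, entry therefore needs a resting wedge of at least 15 mmHg or a peak wedge of at least 25 mmHg.

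Design & Procedures gives the order of events: "Following a baseline invasive (right heart catheterization) cardiopulmonary exercise testing (CPX) patients will undergo unilateral celiac plexus block", "followed by repeat hemodynamic testing in the following 90 minutes". The schedule of events shows one right heart catheterization and one invasive CPX before the block. The table columns are broken in the text available, but the nerve-block section places the later invasive CPX at 4 weeks. The study is open-label and every subject is blocked.

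The dose step for subjects 5 and 6 depends on the 4-week result: "Satisfactory efficacy is defined as >25% reduction with exercise wedge pressure". The reference reading is not named, nor is the way two patients' results are combined. Data Analysis & Statistical Considerations plans t-tests and says "a two-sided 0.05 level of significance will be used to declare change in pre-and post-procedure variables different". No section describes a repeat baseline or an allowance for regression to the mean.

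**The concern.** A wedge reading is the patient's usual level plus that day's deviation. Admitting patients because the reading is high over-represents upward deviations, and those do not carry over to a reading four weeks later. The average wedge then falls even if the block does nothing, always in the direction that favours it.

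Two of the three primary objectives (cardiac preload, and hemodynamics during exercise) are read from these pressures. The bias enters the t-test of change against zero and, through single-patient results, the efficacy call used for subjects 5 and 6. Without a concurrent control, the data cannot separate a modest real fall from this artefact.

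**Working it through.** The plan states no power, effect size or variance, so there is no figure of its own to reproduce. The check asks what the entry rule does when the block has no effect.

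**Inputs from the documents.** Entry if rest ≥15 or peak ≥25 mmHg; one pre-block session; no control arm; two-sided 0.05; dosing steps naming subjects 1 to 6. The test is taken as paired, which the plan does not say. The lower inotrope cut-offs were not modelled.

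**Assumed inputs.** Peak mean 22-28 mmHg, SD 8; resting mean 12-16 mmHg, SD 6; rest/peak correlation 0.7; between-day reliability R of 0.5-0.85; rest/peak correlation of the day errors 0.5.

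**Closed-form check, as if selection were on peak wedge alone.** Spurious fall = (1 − R) × S × φ(a)/(1 − Φ(a)), with a = (25 − mean)/S.
- Mean 25, S = 8: a = 0 and φ/(1 − Φ) = 0.399/0.5 = 0.798. Fall = 0.15 × 8 × 0.798 = 0.96 mmHg at R = 0.85, and 0.5 × 8 × 0.798 = 3.19 mmHg at R = 0.5.
- Mean 32, S = 8: a = −0.875 and the ratio is 0.272/0.809 = 0.336. Fall = 0.40 mmHg at R = 0.85 and 1.34 mmHg at R = 0.5.

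The actual rule also admits patients on resting wedge alone. They are selected on exercise wedge only indirectly, so the real bias is smaller.

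**Simulation of the rule as written, no treatment effect.** 2,000,000 draws per setting. Patients are kept if rest ≥15 or peak ≥25; week 4 is redrawn with the same true value and a new day error; the paired t-test is run in sets of six.

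| Quantity (exercise wedge) | Peak mean 22-28, rest 12-16 | Means near 32/18 |
|---|---|---|
| Spurious mean fall | about 0.4-2.9 mmHg (1.4-10%) | 0.3-0.9 mmHg |
| Two-sided error, n = 6 (nominal 5%) | about 5.5-12% | 5.2-5.6% |

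At n = 20 the error under the first set of means is about 7-37%. The inflation grows with n because the bias stays fixed while the standard error shrinks.

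**Second set of assumptions.** Means (rest/peak) 12/22, 15/27 and 18/32 mmHg; between-patient SD 5/6.5; within-patient SD 2/3, 3/5 and 4/6. The fall is 0.2-2.7 mmHg (0.7-9.6%), with error 5.2-10.3% at n = 6 and 5.4-29.5% at n = 20. With selection switched off the error is 4.7-5.2%, so selection is the cause.

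**Chance that one patient shows a >25% fall with no effect (first set of assumptions).**
- Qualifying reading as baseline: 4-28%.
- Independent separate-day baseline: 3-19%.
- Contribution of selection: 4.1 − 3.1 = 1.0 point at the low end and 28.0 − 18.7 = 9.3 points at the high end. The remaining two-thirds or more (18.7/28.0 = 67%; 3.1/4.1 = 76%) is measurement noise.

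**Same-day readings.** If half the within-patient error variance is shared within a day, a same-day repeat carries about half the bias. In the second set's middle case (15/27 mmHg, within-patient SD 3/5), 1.22 mmHg becomes about 0.6 mmHg.

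**The case against.** The strongest reply concerns size. Every variance input is assumed, and the first set of means straddles the cut-offs, where the bias is largest. Entry also requires NYHA 2-3 disease and an HF hospitalization, ER visit or IV diuretic use within 12 months, and the Background describes marked pressure rises on exercise. If screened patients sit well above the cut-offs, or wedge is very repeatable, the bias is close to nothing. This stands, and it is why the result is given as a range.

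Materiality also counts. This is a pilot for feasibility, safety and dose finding with mainly descriptive statistics, and the 25% rule affects only one dose step. That limits the weight of the point but does not remove it, because the plan does test change at 0.05.

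Three stronger readings are tempting and not supported.
- A reader might infer that regression to the mean could by itself produce the 25% fall, or that the whole 4-28% is due to selection. The mean fall is at most about 10%, and most of that chance is noise that an independent baseline would not remove.
- A reader might take it as stated that the 25% rule uses the qualifying reading. The plan names no reference; this is inferred from there being only one pre-block session.
- A reader might require both thresholds for entry, which under the second set of assumptions raises the fall to 0.5-4.4 mmHg. The exclusion as worded removes only patients who miss both. The sentence is partly garbled, but the joining of the two limits is legible.

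The comparison within 90 minutes should not be treated like week 4; it is less affected if error is shared within a day.

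**Conclusion.** The point holds as a modest one. One pre-block session both selects the patient and is the only available baseline, with no control arm, so the week-4 change is biased in favour of the block. The direction was the same in every setting examined.

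The size depends on assumptions that the documents cannot settle. A spurious exercise-wedge fall of up to about 3 mmHg, and an n = 6 error of up to about 12%, are plausible if typical wedge values lie near the cut-offs; both are negligible if they lie well above. Six is only the number of subjects named in the dosing steps, and a larger study would show more inflation. The bias does not invalidate the 25% rule, but it means that a small mean fall at week 4 cannot by itself be read as a block effect. Correcting this is a worthwhile, inexpensive improvement and not a condition for the study to proceed.

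**What to change.** 1. Take at least two resting wedge readings before the block, with the catheter already in place. Use the first for eligibility and the later one or ones as the resting baseline in the pre/post test.
2. For week-4 exercise wedge, name the baseline reading. Pre-specify a sensitivity analysis that subtracts the expected regression to the mean over a stated reliability range, for example 0.5-0.85. Do not report a mean fall within that range as evidence of an effect.
3. Report single-patient results on the 25% rule with the expected no-effect rate beside them.

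No dose, eligibility cut-off or efficacy threshold changes.

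The cost is one more resting reading per patient and some analysis work. There are limits. A same-day replicate removes only part of the resting bias, about half if half the error is shared within a day. It does nothing for exercise wedge, where the correction is a range and not an estimate. The reported fall will be slightly smaller.

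Implanted-sensor readings should not stand in as a wedge baseline. The criteria admit "Patients with or without Cardiomems device implanted", so the sensor is optional, and the documents do not show that it measures wedge.
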